 Abnormality present but explained entirely by non-GVHD documented cause (specify): _____				
GI Tract Check all that apply:	 No symptoms	 Symptoms without significant weight loss* ( $<5\%$ )	 Symptoms associated with mild to moderate weight loss* (5-15%) OR moderate diarrhea without significant interference with daily living	 Symptoms associated with significant weight loss* $>15\%$ , requires nutritional supplement for most calorie needs OR esophageal dilation OR severe diarrhea with significant interference with daily living
 Esophageal web/ proximal stricture or ring  Dysphagia  Anorexia  Nausea  Vomiting  Diarrhea  Weight loss $\geq 5\%$ *  Failure to thrive				
 Abnormality present but explained entirely by non-GVHD documented cause (specify): _____				
LIVER	 Normal total bilirubin and ALT or AP $< 3 \times \text{ULN}$	 Normal total bilirubin with ALT $\geq 3 \text{ to } 5 \times \text{ULN}$ or AP $\geq 3 \times \text{ULN}$	 Elevated total bilirubin but $\leq 3 \text{ mg/dL}$ or ALT $> 5 \text{ ULN}$	 Elevated total bilirubin $> 3 \text{ mg/dL}$
 Abnormality present but explained entirely by non-GVHD documented cause (specify): _____				
LUNGS** Symptom score:	 No symptoms	 Mild symptoms (shortness of breath after climbing one flight of steps)	 Moderate symptoms (shortness of breath after walking on flat ground)	 Severe symptoms (shortness of breath at rest; requiring $O_2$ )
Lung score: % FEV1 	 FEV1 $\geq 80\%$	 FEV1 60-79%	 FEV1 40-59%	 FEV1 $\leq 39\%$
Pulmonary function tests  Not performed  Abnormality present but explained entirely by non-GVHD documented cause (specify): _____				

	SCORE 0	SCORE 1	SCORE 2	SCORE 3																																

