11.2.3 Signs and symptoms of cGvHD at baseline

Derivation

Derived variable	Definition
Liver score	
The liver score is defined as a combination of Total bilirubin, ALT (SGPT) and AP (ALK) as follows:
 
Score 0: Normal total bilirubin and ALT < 3 ULN and AP < 3 ULN
 
Score 1: Normal total bilirubin with ALT ≥ 3 to 5 ULN or AP ≥ 3 to 5 ULN
 
Score 2: Elevated total bilirubin (> 1 ULN) but ≤ 3 mg/dL or ALT ≥ 5 ULN or AP ≥ 5 ULN
 
Score 3: Elevated total bilirubin > 3 mg/dL
 
Missing if at least one missing serum chemistry

Involved sites number	Number of sites or organs with a score ≥ 1 at baseline (V1)

The following table will be presented:

Variable	Statistics / Modality	Safety Population (N = XX)
NIH scoring of cGVHD		
Scoring of chronic GVHD (NIH criteria)	
Score 0: Asymptomatic and fully active (ECOG 0, KPS or LPS 100%)
 
Score 1: Symptomatic, fully ambulatory, restricted only in physically strenuous activity (ECOG 1, KPS or LPS 80-90 %)
 
Score 2: Symptomatic ambulatory, capable of selfcare,
	
n/N (XX.X%)
 
n/N (XX.X%)
 
n/N (XX.X%)

	> 50 % of walking hours out of bed (ECOG 2, KPS or LPS 60-70 %)	
	Score 3: Symptomatic, limited self-care > 50 % of waking hours in bed (ECOG 3-4, KPS or LPS < 60 %)	n/N (XX.X%)
	Missing	n
Skin – Abnormalities present but explained entirely by non-GvHD documented cause	No	n/N (XX.X%)
	Yes	n/N (XX.X%)
	Missing	n
	Score 0: No BSA involved	n/N (XX.X%)
	Score 1: 1-18% BSA	n/N (XX.X%)
Skin score	Score 2: 19-50% BSA	n/N (XX.X%)
	Score 3: > 50% BSA	n/N (XX.X%)
	Missing	n
Mouth – Abnormalities present but explained entirely by non-GvHD documented cause	No	n/N (XX.X%)
	Yes	n/N (XX.X%)
	Missing	n
	Score 0: No symptoms	n/N (XX.X%)
	Score 1: Mild symptoms with disease signs but not limiting oral intake significantly	n/N (XX.X%)
Mouth score	Score 2: Moderate symptoms with disease signs with partial limitation or oral intake	n/N (XX.X%)
	Score 3: Severe symptoms with disease signs on examination with major limitation or oral intake	n/N (XX.X%)
	Missing	n

Lung – Abnormalities present but explained entirely by non-GvHD documented cause	No	n/N (XX.X%)
	Yes	n/N (XX.X%)
	Missing	n
Lung score + FEV1	Score 0: No symptoms	n/N (XX.X%)
	Score 1: Mild symptoms (shortness of breath after climbing one flight of steps)	n/N (XX.X%)
	Score 2: Moderate symptoms (shortness of breath after walking on flat ground)	n/N (XX.X%)

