	Score 3: Severe symptoms (shortness of breath at rest: requiring 0)	n/N (XX.X%)
Eyes – Abnormalities present but explained entirely by non-GvHD documented cause	Missing	n
	No	n/N (XX.X%)
	Yes	n/N (XX.X%)
Eyes score	Missing	n
	Score 0: No symptoms	n/N (XX.X%)
	Score 1: Mild dry eye symptoms not affecting ADL	n/N (XX.X%)
	Score 2: Moderate dry eye symptoms partially affecting ADL without new vision impairment due to KCS	n/N (XX.X%)
Gastro-intestinal – Abnormalities present but	Score 3: Severe eye symptoms significantly affecting ADL or unable to work because of ocular symptoms of loss or vision due to KCS	n/N (XX.X%)
	Missing	n
	No	n/N (XX.X%)
Yes	Yes	n/N (XX.X%)

Gastro-intestinal score	explained entirely by non-GvHD documented cause	Missing	n
		Score 0: No symptoms	n/N (XX.X%)
		Score 1: Symptoms without significant weight loss (< 5 %)	n/N (XX.X%)
		Score 2: Symptoms associated with mild to moderate weight loss (5-15 %) OR moderate diarrhea without significant interference with daily living	n/N (XX.X%)
		Score 3: Symptoms associated with significant weight loss > 15 %, requires nutritional supplement for most calorie needs OR esophageal dilation OR severe diarrhea with significant interference with daily living	n/N (XX.X%)
Liver score	Liver – Abnormalities present but explained entirely by non-GvHD documented cause	Missing	n
		No	n/N (XX.X%)
		Yes	n/N (XX.X%)
		Missing	n
		Score 0: Normal total bilirubin and ALT or AP < 3 ULN	n/N (XX.X%)
		Score 1: Normal total bilirubin with ALT \geq 3 to 5 ULN and AP \geq 3 to 5 ULN	n/N (XX.X%)
		Score 2: Elevated total bilirubin (> 1 ULN) but ≤ 3 mg/dL or ALT ≥ 5 ULN or AP ≥ 5 ULN	n/N (XX.X%)
		Score 3: Elevated total bilirubin > 3 mg/dL	n/N (XX.X%)
Joint and fascia – Abnormalities present but	Missing	n	
	No	n/N (XX.X%)	

explained entirely by non-GvHD documented cause	Yes	n/N (XX.X%)
	Missing	n
	Score 0: No symptoms	n/N (XX.X%)
	Score 1: Mild tightness of arms or legs, normal or mild decreased range of motion (ROM) AND not affecting ADL	n/N (XX.X%)
	Score 2: Tightness of arms and legs OR joints contractures, erythema thought due to fasciitis, moderate decrease ROM AND mild to moderate limitation of ADL	n/N (XX.X%)
	Score 3: Contractures WITH significant decrease of ROM AND significant limitation of ADL (unable to tie shoes, button shirts, dress self, etc...)	n/N (XX.X%)
	Missing	n
Involved sites number		
Involved sites number	N (N Missing)	XX (XX)
	Mean ± SD	X.X ± X.X
	Median [Min ; Max]	X [X ; X]

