11.4.2 Secondary Endpoint analyses

11.4.2.1 Response by organ

The proportion of response at 6 months (Complete, partial or progressive) will be estimated and presented for each organ. No response is evaluated for an organ when no abnormalities is present at V1, except progressive disease.

Derivation

Derived variables	Definition
Complete response for each organ	Cf Appendix 1 “Evaluation de la réponse – 19OCT2020”
Partial response for each organ	
Progressive disease	
Organ not involved at any moment	

The following table will be presented:

Organ	Response at M6	FAS Population (N = XX)
Organ 1	Complete response	n/N (XX.X%)
	Partial response	n/N (XX.X%)
	Progressive disease	n/N (XX.X%)
	Organ not involved at any moment	n/N (XX.X%)

This table will be completed for skin, mouth, lung, eyes, gastro-intestinal, liver and joint & fascia.

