17. APPENDICES

17.1 RESPONSE CALCULATION ALGORITHM

Etude GMED_16_001 : Evaluation des réponses complètes et partielles – 19/10/2020

Les réponses sont définies comme (règles de calcul basées sur le protocole et l'article Lee et al)

- Complete response at a visit: Lorsque tous les scores de « cGVHD activity assessment form A » des organes suivants sont à 0 ou que la variable "abnormalities present but explained entirely by non-GVHD documented cause » soit égale à Oui.

Détails :

Si une valeur est manquante pour un des organes atteints lors de la visite V1, la réponse ne peut pas être considérée comme complète. le fait que la valeur est manquante sera documentée.

Si une valeur à la visite d'intérêt est manquante sur un organe non atteint lors de la visite V1, la réponse complète peut être établie, car les réponses complètes ou partielles ne sont établies que sur les organes atteints à V1.

Si « abnormalities present but explained entirely by non-GVHD documented cause » = Oui pour un organe à la visite considérée, le score de cet organe n'est pas corrigé et cet organe n'est pas considéré pour l'évaluation de la réponse complète. cela ne créera pas de valeur manquante pour cet organe et n'empêchera pas la réponse d'être considérée comme complète si les informations sur les autres organes sont disponibles.

- BSA=0 ET skin features=0

M6_GVHD_A_S (préfixe M6 ou C1W6, W14, M9 et M12 selon la visite considérée)

M6_GVHD_A_S_F_S

M6_GVHD_A_S_ABN

- Eyes=0

M6_GVHD_A_E

M6_GVHD_A_E_ABN

- Gastrointestinal=0 (pour chacun des 3 scores : Gastro-oesophageal, Gastro-upper, Gastro-lower)

M6_GVHD_A_GASTRO1

M6_GVHD_A_GASTRO2

M6_GVHD_A_GASTRO3

M6_GVHD_GAST_ABN

- Mouth=0 (considérer la somme des 3 scores : Erythema, Lichenoid, Ulcers)

M6_GVHD_A_MOUTH1
 M6_GVHD_A_MOUTH2
 M6_GVHD_A_MOUTH3
 M6_GVHD_MTH_ABN

Joint and fascia =0

M6_GVHD_A_J
 M6_GVHD_A_J_ABN

Liver : les 3 valeurs (Bilirubine, ALAT et PAL) sont en dessous des ULN (Unité limite supérieure) si le score hépatique était >0 à V1 (table 1 et annexe du protocole)

.<M6_GVHD_A_L_SGPT_V<=M6_GVHD_A_L_SGPT_U_V
 .<M6_GVHD_A_L_ALK_V<=M6_GVHD_A_L_ALK_U_V
 M6_GVHD_LIV_ABN

Le score à V1 est calculé comme :

Score = 0 : Bilirubine normale WITH ALAT AND PAL < 3 UNL

(.<V1_GVHD_A_L_BILI_V<=V1_GVHD_A_L_BILI_U_V et
 .<V1_GVHD_A_L_SGPT_V<3* V1_GVHD_A_L_SGPT_U_V et
 .<V1_GVHD_A_L_ALK_V<3* V1_GVHD_A_L_ALK_U_V)

Score = 1 : Bilirubine normale WITH 3 UNL<=ALAT < 5 UNL AND 3 UNL <=PAL<5 UNL

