Score = 2 : Bilirubine élevée (>1*ULN) mais <= à 3 mg/dL OR ALAT >= 5 UNL OR PAL >=5 UNL (non mentionné dans article NIH).

Score = 3 : Bilirubine élevée > à 3 mg/dL

Lung : si FEV1 >=80% et FEV1<70 à V1. et dans le cas où la valeur de FEV1 est manquante, si le score est égal à 0

M6_GVHD_A_LU_FEV1_V>= 80
 missing(M6_GVHD_A_LU_FEV1_V) and M6_GVHD_A_L=0
 M6_GVHD_A_L
 M6_GVHD_A_L_ABN

Calcul de réponse par organe :

Aucun calcul de réponse **par organe** (complète, partielle ou progression) n'est effectué si :

- « abnormalities present but explained entirely by non-GVHD documented cause » = Oui pour un organe à la visite considérée
- CR_*organe*, PR_*organe* et PD_*organe* sont alors mis à . (manquant)

Aucun calcul de réponse complète ou partielle **par organe** n'est effectué si :

- l'organe n'est pas atteint à V1 ou abnormalities present but explained entirely by non-GVHD documented cause » = Oui pour un organe à la visite V1.
- la progression est recherchée même si pas d'atteinte à V1
- CR_*organe* et PR_*organe* sont alors mis à . (manquant)

- **Partial response by organ:** en se basant sur les mêmes scores et en s'intéressant aux diminutions (ou augmentations) entre V1 (mêmes variables qu'indiquées précédemment mais qui commencent par « V1 » au lieu de « M6 ») et la visite considérée (M6, W6, W14, M9 ou M12)

- une diminution d'1 point pour les scores sur des échelles de 0 à 4 pour : Skin BSA, Skin features, Eyes, Joints, Gastro-oesophageal, Gastro-upper, Gastro-lower,
- une diminution de 2 points pour la somme des 3 sous-scores pour Mouth
- pour Lung, une augmentation entre V1 et la visite d'au moins 10% sur FEV1 avec FEV1 à V1 <70. Dans le cas de FEV1 manquants à V1 et ou M6, une diminution d'1 point sur le score 'lungs'
- pour Liver, (Bilirubine, ALAT ou PAL),
- si les valeurs à M6 sont en dessous des normales, la réponse est considérée Complète
- sinon la recherche d'une réponse partielle est effectuée : diminution de 50% de la valeur initiale
 Le ratio est calculé ainsi : $(M6-V1/V1)*100$ et si le ratio est inférieur à -50 (mais pas de progression pour une des autres valeurs), il y a une réponse partielle

Global Partial response: au moins une réponse partielle sur un organe et avec une absence de progression pour un autre site

- **Progressive disease by organ:**

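### The liver rule in SAP 17.1 requires both ALT and AP at 3 to <5 ULN for score 1, so a baseline liver with only one enzyme in that band gets no score and, on the natural reading, is left out of computed CR and PR

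*SAP*

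**What the plan says.** The SAP defines the baseline liver score in several places, and they do not agree. ALAT is ALT, PAL is alkaline phosphatase (AP), and UNL is ULN.

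- **SAP 17.1, score 0:** "Score = 0 : Bilirubine normale WITH ALAT AND PAL < 3 UNL".
- **SAP 17.1, score 1:** "Bilirubine normale WITH 3 UNL<=ALAT < 5 UNL AND 3 UNL <=PAL<5 UNL".
- **SAP 17.1, score 2:** raised bilirubin up to 3 mg/dL, "OR ALAT >= 5 UNL OR PAL >=5 UNL". Score 3 is bilirubin above 3 mg/dL.
- **SAP 11.2.3, derivation row:** "Score 1: Normal total bilirubin with ALT ≥ 3 to 5 ULN or AP ≥ 3 to 5 ULN".
- **SAP 11.2.3, table shell:** the same score 1 is printed with "3 to 5 ULN and AP", so the section contradicts itself.
- **Protocol Appendix 2, and its copy in the SAP appendices:** score 1 joins the ALT and AP conditions by *or*.
- **Response determination table (protocol Table 4, repeated in the SAP):** liver CR means normalisation after at least one of the three analytes had been raised.

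In 17.1 the score acts as a gate. Normal liver values are a condition of CR only "si le score hépatique était >0 à V1". Organ-level CR and PR are set to missing if the organ was not involved at V1, but progression is searched for regardless. SAP 11.4.2.1 puts the gate differently: "No response is evaluated for an organ when no abnormalities is present at V1, except progressive disease".

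**The concern.** A severity scale used as a gate has to be exhaustive. Here score 0 needs both enzymes low, score 1 needs both in the middle band, and score 2 needs one enzyme high or raised bilirubin. A single enzyme in the middle band fits none of these. The protocol counts that liver as involved, so the algorithm would depart from the protocol's response definition for such a patient. The computed response is the rule-based check on an open-label endpoint judged by the investigator, and it is useful only if it applies the protocol's criteria.

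**Working it through.** No published figure is at stake; the check is whether each rule set covers every laboratory pattern.

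**1. Coverage.** The 17.1 rules and the 11.2.3 derivation row were applied to a grid: bilirubin {normal, raised but ≤3 mg/dL, >3 mg/dL} × ALT {1, 2, 4, 6 ULN} × AP {1, 2, 4, 6 ULN}, taking the highest matching score. That is 3 × 4 × 4 = 48 cells. The two rule sets differ in four cells, all with normal bilirubin:

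| ALT (ULN) | AP (ULN) | 17.1 score | 11.2.3 derivation score |
|---|---|---|---|
| 4 | 1 | none | 1 |
| 4 | 2 | none | 1 |
| 1 | 4 | none | 1 |
| 2 | 4 | none | 1 |

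The other 44 cells are scored, and identically. An isolated enzyme at 6 ULN scores 2 under both. The gap is therefore exactly this: normal bilirubin, one enzyme at 3 to <5 ULN, the other <3 ULN.

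**2. Consequence in 17.1.** Take a patient with normal bilirubin, ALT 4 ULN and AP 1 ULN at V1.

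- *Improvement.* 17.1 computes the change as (M6 − V1)/V1 × 100 and calls a liver PR below −50. The threshold is ALT = 2 ULN: (2 − 4)/4 × 100 = −50. A fall to below 2 ULN that is still above normal is a liver PR if V1 is scored 1. If V1 has no score, liver PR is missing.
- *No improvement.* If ALT stays at 4 ULN and every other organ clears, a V1 score of 1 makes the liver block CR and the patient is a PR. With no V1 score the liver condition is not invoked and the patient is a CR.
- *Worsening.* Progression is M6 − V1 > 2 × ULN, here ALT above 4 + 2 = 6 ULN. This uses laboratory values and is searched for even without V1 involvement, so it is unaffected.

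**3. Where it feeds.** The main analysis (SAP 11.4.1.1) uses the investigator's judgement. The computed response is used in sensitivity analyses b and d (SAP 11.4.1.2) and their tables and forest plots. The organ-level rules feed the by-organ table (SAP 11.4.2.1), which is listed for FAS and PP. The number of involved sites is derived in 11.2.3, alongside the liver score that uses *or*.

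**4. After correction.** With OR in the score 1 rule, all 48 cells are scored. The four gap cells become score 1, as in the 11.2.3 derivation row and protocol Appendix 2.

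**The case against.** The strongest reply is that the consequence is inferred. The SAP has no rule saying that an unmatched pattern means not involved. SAP 11.4.2.1 withholds CR and PR only where no abnormality was present at V1, and ALT at 4 ULN is an abnormality. Liver PR itself is computed from laboratory values, and 17.1 cites the protocol annex for the liver score. A programmer could reach the right answer despite the text. This stands as a limit on certainty. It does not remove the defect, because 17.1 makes the CR condition depend on a score above 0 and an absent score does not meet that.

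It may also be said that the AND was deliberate. That is unlikely: 17.1 marks its AP clause in score 2 as absent from the NIH article but carries no such note for the AND.

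Four stronger readings are tempting, and the documents do not support them:

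- *Any isolated ALT or AP elevation is unscored.* Values of 5 ULN or more score 2.
- *The liver drops out of response assessment altogether.* Progression is still assessed.
- *The primary analysis or its organ-number subgroup is affected.* The first rests on the investigator's judgement. The second is derived in 11.2.3 with *or*, and would be touched only if the code followed 17.1 or the shell.
- *Each such patient moves the computed response rate by 1/24 = 4.2 or 1/21 = 4.8 points.* That holds only if responder status changes. Global PR needs one improving organ without progression elsewhere. Protocol 7.1.1 requires a diagnostic or distinctive manifestation, and protocol Appendix 1 lists liver findings only as common features, so another site will be involved.

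**Conclusion.** The inconsistency is real, and 17.1 is wrong as written. For normal bilirubin with exactly one enzyme at 3 to <5 ULN, it assigns no score where the protocol and the 11.2.3 derivation assign 1. On the natural reading the liver then leaves CR and PR assessment but stays in progression assessment.

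The reach is narrow: the computed response in sensitivity analyses b and d, and the by-organ table. Where another scored organ was involved at baseline, CR+PR changes only if the liver is the sole improving organ, and the error is then a lost responder. Otherwise the main effect is to move a patient from PR to CR. The documents do not say how many patients have this pattern, and it could be none. The conclusion assumes that an unscored liver is handled as not above 0 at V1. It should be corrected because it distorts the rule-based check, not because it threatens the primary result.

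**What to change.** In SAP 17.1, define liver score 1 as normal bilirubin with at least one of ALT and AP at 3 to <5 ULN and neither at 5 ULN or more. Scores 0 to 3 are then exhaustive for complete laboratory data. Make the same correction in the 11.2.3 table shell so that it matches its own derivation row. While there, check the shell's score 0 label, which joins the enzymes by *or* where the derivation row requires both to be below 3 ULN.

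The cost is one operator in the text and code of 17.1, one line in the shell, and a rerun of the computed-response and by-organ outputs if they have already been programmed. No new data are needed. A listing of patients whose V1 liver score changes would show whether the point had any practical effect.

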### **7.3.2 Treatment plan**

#### ***7.3.2.1 Arsenic trioxide therapy***

As soon as the diagnosis of chronic GvHD requiring systemic immunosuppressive therapy is confirmed, patients will receive in addition to cyclosporine A (if relevant) and corticosteroids 1 mg/kg/day, ATO 0,15 mg/kg/day over a 4 weeks period (one cycle).

The treatment plan is indicative, but it is important to respect the number of 11 perfusions per cycle. In the case of a temporary discontinuation of ATO therapy for medical or other reasons, the canceled infusions will be scheduled as soon as possible.

- Week 1: day 1 to 5
- Week 2: 3 times per week (example: day 8, 10 and 12)
- Week 3: 2 times per week (example: day 15 and 17)
- Week 4: 1 time per week (example: day 24)

ATO should be administered within 10 days of starting prednisone 1mg/kg/day. Follow-up dates for response assessment and laboratory tests relate to the date of ATO infusion. Patients in partial response after the 1st cycle of ATO will be eligible to receive a second cycle of ATO as consolidation therapy. A delay of 8 weeks to a maximum of 11 weeks (from the first infusion of ATO) will be observed between the two cycles of ATO therapy.

Response definition is as follows:

- Complete remission (CR) is defined as complete disappearance of any sign of chronic GvHD
- Partial remission (PR) is defined as improvement of 1 or more point on a 4 to 7-point scale or an improvement of 2 or more points on a 10 to 12-points scale in at least 1 organ or site without progression in any other organ or site. For patients with BOS, an absolute improvement in %FEV1 of 10% predicted or more (eg, 50% to 60%) is considered a PR as long as the initial % FEV1 is < 70%. Normalization ( $\geq 80\%$ ) is considered a CR.
- Progressive disease (PD) is defined as at least one organ system has worsened by at least one stage without improvement of any other organ systems from baseline:
  - For skin, eye, esophagus, and upper and lower gastro-intestinal (GI) tract, a worsening of 1 point or more on the 0 to 3 scale is considered progression, except a change from 0 to 1, which is considered trivial progression since it often reflects mild, nonspecific, intermittent, self-limited symptoms and signs that do not warrant a change of therapy.

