  - For joint/fascia, a worsening of 1 point or more on the 0 to 3 scale is considered progression, even if from 0 to 1, because a change to score 1 was considered meaningful progression that would prompt a change in therapy. For joints assessed by the photographic range of motion, a worsening of 1 or more points for the 7-point scales and 1 or more points for the 4-point scale is considered progression.
  - For mouth, a worsening of 2 or more points on the 1-point scale indicates

progression.

- Worsening of liver GvHD is defined by an increase of 2 or more times the upper limit of normal for the assay for alanine transaminase, alkaline phosphatase, or total bilirubin.
- For patients with lung involvement, absolute worsening of FEV1 by 10% predicted or more (eg, 50% to 40%) is considered progression, as long as the final %FEV1 is < 65% (because initial %FEV1 must be < 75% to establish the diagnosis of lung involvement). If PFTs are not available, then worsening of the clinical lung score based on symptoms by 1 or more points should be scored as progression, except from score 0 to 1, which is considered trivial progression because of its lack of specificity for lung chronic GvHD.
- Mixed response is defined as CR or PR in at least one organ accompanied by progression in another organ
- Unchanged: outcome that do not meet criteria for CR, PR, PF or mixed response are considered unchanged

Response determination for chronic GvHD is indicated in the table below:

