**Table 4. Response determination for chronic GvHD**

Organ	Complete Response	Partial Response	Progression
Skin	NIH Skin Score 0 after previous involvement	Decrease in NIH Skin Score by 1 or more points	Increase in NIH Skin Score by 1 or more points, except 0 to 1
Eyes	NIH Eye Score 0 after previous involvement	Decrease in NIH Eye Score by 1 or more points	Increase in NIH Eye Score by 1 or more points, except 0 to 1
Mouth	NIH Modified OMRS 0 after previous involvement	Decrease in NIH Modified OMRS of 2 or more points	Increase in NIH Modified OMRS of 2 or more points
Esophagus	NIH Esophagus Score 0 after previous involvement	Decrease in NIH Esophagus Score by 1 or more points	Increase in NIH Esophagus Score by 1 or more points, except 0 to 1
Upper GI	NIH Upper GI Score 0 after previous involvement	Decrease in NIH Upper GI Score by 1 or more points	Increase in NIH Upper GI Score by 1 or more points, except 0 to 1
Lower GI	NIH Lower GI Score 0 after previous involvement	Decrease in NIH Lower GI Score by 1 or more points	Increase in NIH Lower GI Score by 1 or more points, except from 0 to 1
Liver	Normal ALT, alkaline phosphatase, and Total bilirubin after previous elevation of 1 or more	Decrease by 50%	Increase by 2 × ULN
Lungs	- Normal %FEV1 after previous involvement - If PFTs not available, NIH Lung Symptom Score 0 after previous involvement	- Increase by 10% predicted absolute value of %FEV1 - If PFTs not available, decrease in NIH Lung Symptom Score by 1 or more points	- Decrease by 10% predicted absolute value of %FEV1 - If PFTs not available, increase in NIH Lung Symptom Score by 1 or more points, except 0 to 1
Joints and fascia	Both NIH Joint and Fascia Score 0 and P-ROM score 25 after previous involvement by at least 1 measure	Decrease in NIH Joint and Fascia Score by 1 or more points or increase in P-ROM score by 1 point for any site	Increase in NIH Joint and Fascia Score by 1 or more points or decrease in P-ROM score by 1 point for any site
Global	Clinician overall severity score 0	Clinician overall severity score decreases by 2 or more points on a 0-10 scale	Clinician overall severity score increases by 2 or more points on a 0-10 scale

ULN indicates upper limit of normal.

- Resistance is defined as lack of a CR/PR 2 weeks after the last ATO infusion,

[figure not shown]
requirement for alternative therapy or death from GvHD before the last ATO infusion

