- peau, yeux, œsophage, tractus gastro-intestinal supérieur et inférieur : augmentation 1 point ou plus sur échelle de 0 à 3 = progression SAUF si changement de 0 à 1 (progression non spécifique)
- Joint: augmentation d'1 point ou plus = progression
- bouche : changement de 2 points ou plus sur la somme des 3 sous-scores

- pour Lung, diminution de 10 % avec FEV1 à V1 < 75% . Dans le cas de FEV1 manquants, augmentation d'1 point ou plus *SAUF* si changement de 0 à 1 (progression non spécifique)

- pour Liver, si l'une des valeurs à M6 est au-dessus de la normale pour Bilirubine, ALAT ou PAL, la recherche d'une progression est effectuée : la différence M6 – V1 est calculée et si la différence est supérieure à 2*ULN, il y a Progression.

Global progressive disease : si au moins un site avec une progression

Mixed response: si **Progressive disease** sur au moins un organe et **Partial response** sur au moins un autre

Extraits du protocole :

Table 4. Response determination for chronic GvHD (extrait du protocole)

Organ	Complete Response	Partial Response	Progression
Skin	NIH Skin Score 0 after previous involvement	Decrease in NIH Skin Score by 1 or more points	Increase in NIH Skin Score by 1 or more points, except 0 to 1
Eyes	NIH Eye Score 0 after previous involvement	Decrease in NIH Eye Score by 1 or more points	Increase in NIH Eye Score by 1 or more points, except 0 to 1
Mouth	NIH Modified OMRS 0 after previous involvement	Decrease in NIH Modified OMRS of 2 or more points	Increase in NIH Modified OMRS of 2 or more points
Esophagus	NIH Esophagus Score 0 after previous involvement	Decrease in NIH Esophagus Score by 1 or more points	Increase in NIH Esophagus Score by 1 or more points, except 0 to 1
Upper GI	NIH Upper GI Score 0 after previous involvement	Decrease in NIH Upper GI Score by 1 or more points	Increase in NIH Upper GI Score by 1 or more points, except 0 to 1
Lower GI	NIH Lower GI Score 0 after previous involvement	Decrease in NIH Lower GI Score by 1 or more points	Increase in NIH Lower GI Score by 1 or more points, except from 0 to 1
Liver	Normal ALT, alkaline phosphatase, and Total bilirubin after previous elevation of 1 or more	Decrease by 50%	Increase by 2 × ULN

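### SAP 17.1 puts the protocol's baseline FEV1 <70% limit for lung PR onto lung CR as well, so the written rule conflicts with Table 4 and with the SAP's own variable line

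*SAP*

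**What the plan says.** SAP 17.1 (Response calculation algorithm) gives the lung CR rule in prose as "si FEV1 >=80% et FEV1<70 à V1". If the visit FEV1 is missing, a symptom score of 0 counts instead. The variable lines beneath this read "M6_GVHD_A_LU_FEV1_V>= 80" and "missing(M6_GVHD_A_LU_FEV1_V) and M6_GVHD_A_L=0"; neither contains a V1 value.

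For lung PR the same section requires "une augmentation entre V1 et la visite d'au moins 10% sur FEV1 avec FEV1 à V1 <70". If FEV1 is missing at V1 and/or at the visit, a one-point fall in the symptom score is used. For lung progression it requires "diminution de 10 % avec FEV1 à V1 < 75"%.

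The protocol (section 7.3.2.1, repeated in substance in the synopsis, 9.2 and 9.3) says of a 10-point gain in %FEV1 that it "is considered a PR as long as the initial % FEV1 is < 70"%. A separate sentence then makes normalisation (>=80%) a CR, with no baseline limit. Protocol Table 4 gives lung CR as "Normal %FEV1 after previous involvement". The SAP reprints this entry in 8.2.1 and again at the end of 17.1.

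Two statements bear on lung involvement. The organ scoring table (Protocol Appendix 2, partly reprinted in the SAP) gives score 1 to FEV1 60-79%, and SAP 11.2.3 counts a site as involved from score 1. The protocol's progression rule instead says "because initial %FEV1 must be < 75% to establish the diagnosis of lung involvement".

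**The concern.** SAP 17.1 says that its rules are based on the protocol, yet its lung CR rule carries a condition that the protocol places on lung PR. Since the SAP's PR rule has the same condition, a patient with baseline FEV1 of 70% or more and measured values has no lung response category left, however far FEV1 recovers. The progression rule has a higher baseline limit (<75%), so at 70-74% the same patient can still be scored as worse.

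The agreement of the computed response with the protocol is at stake. In this single-arm trial the main analysis rests on the investigator's judgement of response, and the computed response is the rule-based check on it. The check should apply the protocol's definition. Response by organ (SAP 11.4.2.1) takes its lung row from the same algorithm.

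**Working it through.** The plan states no figure to reproduce here. The check sets the rules side by side and applies them to the same baselines.

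**Rules, with V1 = baseline %FEV1 and M6 = visit %FEV1, both measured**

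| Rule | Source | Condition |
|---|---|---|
| CR, SAP prose | SAP 17.1 | M6 >= 80 and V1 < 70 |
| CR, SAP variable line | SAP 17.1 | M6 >= 80 |
| CR, Table 4 | Protocol Table 4; SAP 8.2.1 and 17.1 | M6 normal (>= 80) and lung previously involved |
| PR | SAP 17.1 | M6 - V1 >= 10 and V1 < 70 |
| Progression | SAP 17.1 | V1 - M6 >= 10 and V1 < 75 |

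**One patient, V1 = 72 and M6 = 90**

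- Table 4: 90 >= 80 after involvement, so CR.
- SAP variable line: 90 >= 80, so CR.
- SAP prose: 90 >= 80 holds but 72 < 70 fails, so not CR.
- SAP PR: 90 - 72 = 18 >= 10 holds but 72 < 70 fails, so not PR.
- If FEV1 instead falls to 62: 72 - 62 = 10 and 72 < 75, so progression.

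**Every integer baseline in the score-1 band (60 to 79, 20 values), with M6 = 80 and M6 = 90; the counts are the same for both**

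| Baseline | CR, Table 4 | CR, variable line | CR, SAP prose | PR, SAP | Progression after a 10-point fall |
|---|---|---|---|---|---|
| 60-69 (10 values) | 10 | 10 | 10 | 10 | 10 |
| 70-74 (5 values) | 5 | 5 | 0 | 0 | 5 |
| 75-79 (5 values) | 5 | 5 | 0 | 0 | 0 |

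The Table 4 column takes involvement as score >= 1. Under the prose, 10 of the 20 baselines reach lung CR; under Table 4 all 20 do. If involvement means FEV1 < 75%, the 75-79 row drops out and 5 of the 15 remaining baselines (70-74) are blocked. These are counts of integer baselines, not of patients.

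**What this does to the global computed response, if lung counts as involved at V1**

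- Lung and skin involved, skin score 2 to 0, FEV1 72 to 90: Table 4 gives global CR. Under the prose, lung is not CR, so global CR fails; the skin improvement without progression elsewhere gives global PR. CR+PR is unchanged.
- Lung the only involved organ, FEV1 72 to 90: Table 4 gives CR; the prose gives no response. Here CR+PR also changes.

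**Where the computed response is used.** SAP 11.4.1.1 takes response from the investigator. SAP 11.4.1.2 b) and d) use the computed response, and 11.4.2.1 uses the organ-level rules.

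**The case against.** The strongest objection is that the <70% term may be the SAP's way of writing previous involvement. The protocol keeps the <70% limit and the normalisation sentence together in one provision for bronchiolitis obliterans syndrome. On that reading, lung at 70% or above is simply not involved at V1, its CR and PR are set to missing, and it does not block a global CR. This reading is possible, and because of it a downward bias in the global computed CR is not established. It does not rescue the text. Lung CR is still not assigned where Table 4 and score >= 1 would assign it, and <70% becomes a third involvement threshold beside score >= 1 (60-79%) and <75%.

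A second objection is that the variable line has no V1 term, so the programmed rule may already match Table 4. The documents do not settle this. The liver variable lines also leave out conditions that their prose states (bilirubin, and the V1 score), so these lines may be partial lists of variables rather than full code. What stands is that prose and variable line give different answers for the same patient.

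Some stronger statements are tempting, and the documents do not support them:

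- A reader might infer that a baseline of 70-79% can never give a lung response. The symptom-score fallbacks allow CR when visit FEV1 is missing and the score is 0, and PR by a one-point fall when FEV1 is missing at V1 and/or the visit. The exclusion holds only for measured FEV1.
- A reader might infer that half of the score-1 band is definitely shut out. With involvement at <75%, the band is 70-74%.
- A reader might put the cost at 4.2 to 4.8 points per patient (1/24 to 1/21). The denominator is assumed, since the size of the full analysis set is not fixed at 21 to 24. For CR+PR the loss also occurs only when no other organ responds.

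**Conclusion.** The point holds as a conflict between the stated lung CR rule in SAP 17.1 and three things: the protocol text, Table 4, and the SAP's own variable line. If the prose governs and FEV1 is measured, a normalised FEV1 from a baseline of 70% up to the involvement threshold yields neither lung CR nor lung PR. At 70-74%, a 10-point fall in the same patient is scored as progression.

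The reach is limited. In sensitivity analyses b) and d) the usual effect would be a global CR recorded as PR; CR+PR changes only when no other organ responds. Both statements assume that lung is treated as involved at V1. The lung row of response by organ is affected directly. A reader might infer that the primary result is at risk, but the main analysis uses the investigator's judgement and does not pass through this rule.

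The documents do not say how many patients had a baseline FEV1 in the affected band. The effect on any reported rate cannot be computed and may be zero. This is a minor but clear correction.

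**What to change.** In SAP 17.1:

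1. Define lung CR as FEV1 >= 80% at the visit after lung involvement at V1, and remove the V1 < 70% term from CR. Keep that term for PR only.
2. State one definition of lung involvement at V1 that reconciles score >= 1 (60-79%) with the <75% wording, and use it in the lung CR rule and in the count of involved sites. Do not simply write <80% into the CR rule: that would contradict the <75% wording and would make a change from 79% to 80% a lung CR.
3. Make the variable lines match the prose, including the V1 involvement condition, and say which governs.

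The cost is a line or two of SAP text and the matching code, plus a decision on the involvement threshold. No new data are needed, as V1 and visit FEV1 are already collected. It would also help to report how many patients had a baseline FEV1 of 70-74% and of 75-79%, so that a reader can see whether the rule mattered.
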